3.9 Inclusion and exclusion criteria

Inclusion criteria

Adult patient above 18 years of age, who has schedule appointment in dental hygienist clinic for scaling and prophylaxis procedure.

Exclusion criteria

Any room have additional mechanical ventilation rather than air conditioner and orthodontic patient will be excluded.

3.10 Variables and Data collection

Measurement devices

2. Digital dust monitor

Particles matter will be measured using Digital dust monitor (model 3443, KANOMAX.USA INC., made in Japan). This device measure particle size that range from 0.1 to 10 Mm using light scattering method (semiconductor laser radiation light source) with flow rate 1 L/min. air is collect through a filter which is built-in in order to eliminate coarse particles. Filter is reusable and it needs approximately 5 minutes cleaning time depending on environment. Minimum, maximum, and average concentration result show among measurement time. Calibration of device will be performed according to manufacture instruction.

3. Microbial air sampler device (sampl'air ASE)

Is considered as active air sampler method which used to collect microorganism onto solid media with flow rate 100 L/ min. Positive hole conversion table should be used in order to counting colony; colony forming units per volume of air (CFU m⁻³).

In this study a specific agar media will be used to collect oral bacteria and fungus.

Outcome variable

Particle count level (difference in PN count[ΔPN ;post-test – pre-test , counts/ m³])
(continuous variable)

Average of oral bacterial concentration before and during procedure

Average of fungus concentration before and during procedure

Microbial air concentration including bacteria and fungus before and during procedure (floor and near to A.C)

Explanatory variable

Categorical variable

Place ,intervention groups, order of patient ,gender and supragingival calculus (mild, moderate, heavy) ,

Continuous variable

time of procedure that staring from the beginning of scaling until finishing of scaling (in minutes), time on day (morning, afternoon), age, year experience of hygienist, distance of room, humidity, and room temperature.

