3.4 Study area and setting

1. This study will be conducted in close rooms at educational hospital, public hospital and private dental clinic. Humidity and temperature will be recorded at the beginning, measuring particles oral bacteria and fungus will be performed 15 minutes before and approximately 15 minutes during scaling and prophylaxes procedure in two opposite quadrants in left side. Additionally 5 minutes will require between two interval to allow cleaning process of filter in Digital dust monitor. Microbial sampler devices will be distributed at several locations in room, three microbial air sampler devices around patient, at 8 o'clock position, 1 o'clock position and 4 o'clock. Another device that will be placed near to air condition and one agar media on the floor to control another microbial agents that could be arising from A.C.. Intervention devices that will be used is EOS where being place on left side of patent to allow comfortable movement of hygienist and suction cone will be away from patient mouth from 10 -15 cm based on manufacture instruction.

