3.11 Statistical consideration

All continuous variables will be express as mean and stander deviation

All categorical variables will be described as frequency and percentage

Difference between baseline and during of procedure measurement intended for particle, oral bacteria, fungus and microbial air concentration will be calculating using pairwise t test.

Difference between each categorical groups and particle, oral bacterial, fungus, and microbial air concentration will be tested using two way ANOVA test or one way ANOVA test

Strength and direction of association between particle count levels and time of procedure will be tested using correlation test

Multiple linear regression model will be built to predict particles count level with entrance value of 0.01 and exit value 0.101. Confidence level of 95% will be computed and p-value less than 0.05 will be considered as significant.

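### The near-A.C. sampler and floor agar are set up as background controls, but are tested as one outcome and never used as controls; the floor count appears to have no CFU/m³ value

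*Combined protocol and SAP*

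**What the plan says.** Section 3.4 (Study area and setting) describes two sets of microbial samples. Near the patient there are "three microbial air sampler devices around patient, at 8 o'clock position, 1 o'clock position and 4 o'clock". Away from the patient, the text reads "Another device that will be placed near to air condition and one agar media on the floor to control another microbial agents that could be" coming from the air conditioner. These last two samples therefore have a stated control purpose.

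Section 3.10 (Variables and Data collection) describes the sampler as an "active air sampler method which used to collect microorganism onto solid media with flow rate 100 L/ min" and gives its result as "colony forming units per volume of air". It gives no flow rate, volume, exposure time or unit for the floor agar. Under the outcome variables it lists four items: particle count, oral bacteria, fungus, and "Microbial air concentration including bacteria and fungus before and during procedure (floor and near to A.C"). Its explanatory variables include place, humidity and room temperature, but no air-conditioner or floor count.

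Section 3.11 (Statistical consideration) puts the fourth item into the before-versus-during t test. For the groups it says that "microbial air concentration will be tested using two way ANOVA test or one way ANOVA test", in the same sentence as particles, bacteria and fungus. The only regression model in that section is for particle count.

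**The concern.** The purpose in section 3.4 and the use in sections 3.10 and 3.11 do not match. Samples taken to separate room sources from the patient's contribution become a fourth outcome, and nothing carries them into the bacterial or fungal comparisons.

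Two things are at stake. First, a significant group difference in this item would have no stated meaning. It could be read as a device effect, as spread of aerosol through the room, or as a background difference between groups. Second, the item is called a concentration, but one of its two locations appears to yield only a colony count per plate. If an analyst combined the locations, the result would have no defined unit, and the plan has no rule that prevents this.

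**Working it through.** The plan states no figure for this outcome, so there is nothing to reproduce. The check is one of units, then of use, then of cost.

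**1. Can each location be expressed in CFU/m³?**

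Input: flow rate 100 L/min (section 3.10). Section 3.4 gives a measurement window of 15 minutes before and about 15 minutes during the procedure. It gives no sampler run time, so I take 1 to 15 minutes as an assumed range.

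Sampled volume in m³ = flow rate × minutes / 1000. Concentration = colonies / volume.

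- 1 minute: 100 × 1 / 1000 = 0.1 m³, so one corrected colony is 1 / 0.1 = 10 CFU/m³.
- 15 minutes: 100 × 15 / 1000 = 1.5 m³, so one corrected colony is 1 / 1.5 = 0.67 CFU/m³.
- Floor agar: no flow rate, hence no volume, hence no CFU/m³. Only colonies per plate for a given exposure is available.

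The near-A.C. reading converts whatever the run time. The floor reading does not convert from anything in the documents.

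**2. How are the readings used?**

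- Section 3.4: both samples are there as a control for other microbial sources.
- Section 3.10: both sit in one outcome item, and neither is an explanatory variable.
- Section 3.11: that item is tested before versus during and between groups. No bacterial or fungal model contains it.

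Testing the item alongside the other three also adds a fourth family of tests at 0.05. As an illustration, assume one independent test per family. The chance of at least one false positive is then 1 − 0.95⁴ = 18.5% with four families and 1 − 0.95³ = 14.3% with three. Readings from one room are unlikely to be independent, so these figures only indicate scale.

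**3. What would using the control cost?**

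Take the stated total of 120 (section 3.7), four groups, a one-way layout and complete data.

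- Residual degrees of freedom: 120 − 4 = 116.
- With the outcome's own pre-procedure value: 115.
- With the pre-procedure near-A.C. reading added: 114.

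Let r be the partial correlation of the near-A.C. reading with the outcome, given group and the outcome's own pre-procedure value. The residual mean square falls when (1 − r²) / 114 < 1 / 115, that is, when r² > 1/115 = 0.0087, or |r| above about 0.09. The documents give no value for r, so the actual gain in precision cannot be stated.

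**The case against.** Four points on the other side have force.

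**No pooling is stated.** A reader might infer that the plan averages or sums the two locations and so mixes units. The text does not support that. The bacterial and fungal outcomes are introduced as averages, while this item is not and has no combination rule. The bracket may simply list two locations to be analysed separately. A reader might also infer that sampler run time would shift the relative weight of the two sources. It would not in the same air, because dividing by volume removes run time. At 20 CFU/m³, 15 minutes collects 30 colonies and 1 minute collects 2, and both return 20 CFU/m³.

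**The passive plate is an inference.** It rests on the contrast between a device and agar media, and on the absence of a flow rate. The layout figure is not available. If an active sampler does run at floor level, the unit point falls away, but the plan should say so.

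**Room air can be a legitimate outcome.** The aim concerns contamination of the clinic's indoor air, the abstract names microbial air among the measurements, and section 3.2 says the extra-oral device cleans the air. A test of these readings could also serve as a balance check. This stands in part: the plan states neither use, and section 3.4 states a control purpose.

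**Bias is already limited.** Random allocation protects the group comparisons from systematic background differences, and the before/during design removes stable room background. This stands in full. Omitting the near-A.C. reading is not shown to bias anything.

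**Conclusion.** The concern holds in a limited form, and it is minor. The near-A.C. and floor readings are described as controls, analysed as one outcome, and not used as controls where they would matter. On the text as it stands, the floor count has no CFU/m³ value and should not be pooled with the near-A.C. reading; that pooling is planned is not established.

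The effect is confined to one of four outcomes and to the adjustment of the bacterial and fungal comparisons. The particle outcome is untouched. The gain from acting is some precision and use of a control that is already planned, not removal of a demonstrated bias.

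This rests on two assumptions: that the floor agar is exposed without a sampler, and that the near-A.C. sampler yields separate bacterial and fungal counts before the procedure. Section 3.10 suggests the second by saying that the item includes both.

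**What to change.** 1. Split the item in section 3.10. Report the near-A.C. reading in CFU/m³ and the floor plate in CFU per plate, with the plate exposed for the same stated time before and during the procedure. Do not average or sum them. If the floor sample is in fact taken with a sampler, say so and give its volume.
2. Reconcile sections 3.4 and 3.10 by labelling both readings as background or room-spread measures, not as evidence of device efficacy. Any test of them in section 3.11 should be described in those terms.
3. In the bacterial and fungal group comparisons, add the matching pre-procedure near-A.C. reading as a covariate (bacterial for bacteria, fungal for fungus), alongside the outcome's own pre-procedure value. Do not adjust for the during-procedure reading, which the device may affect.

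The near-A.C. covariate costs about one degree of freedom per model. The outcome's own pre-procedure value costs one more if it is not already intended. Fixing the plate exposure time changes the field procedure as well as the SAP wording. No extra participants or equipment are needed.

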Effectiveness of Extra- oral Suction Comparing to Other Suction in Reducing Particles Matter and Bioaerosol in Dental Clinic, Randomized Clinical Trial.

NCT05848245

September 15, 2022

[name]

Supervised by

[name], [name], [name]

Content table

.1	Abstract in English	3
.2	Introduction	4
	Background 3.1	4
	Rational of research 3.2	5
	Objective 3.3	5
	MATERIAL AND METHODS .4	5
	Study design 4.1	5
	Intervention devices 4.2	5
	Intervention groups 4.3	6
	Study area and setting 4.4	6
	Assessment 4.5	6
	Study participants 4.6	7
	Sample size 4.7	7
	Sampling technique 4.8	7
	Inclusion and exclusion criteria 4.9	7
	Variables and Data collection 4.10	7
	Statistical consideration 4.11	9
	Ethical consideration 4.12	9
	Limitation and strength 4.13	9
	Devices and setting figure .5	10
.6	References	12

1. Abstract in English

Aerosol particles generated when using dental instrument such as ultrasonic and high air driven handpieces, this aerosol is mixture of blood, saliva, infectious agents, and dental materials. Inhaler dust that range between PM2.5 to PM10 could transferred to the human lung's terminal bronchioles and alveoli that cause a harm effect.

The aim of this study to assess the effectiveness of different dental suction devices that could be contributed to decrease risk of particles count, Bacterial and fungal that arising from patient mouth to indoor air dental clinic

This is a randomized clinical trial will be conducted in three different places: educational hospital, public hospital, and private clinic. In each place 40 subject will be recruited. Measurement including particles count and microorganism will be taken before 15 minutes and during of scaling and prophylaxis procedure to measure particles count, oral bacteria, fungus, and microbial air. In this study will be compared between four intervention groups; Group A with high and low suction only, Group B using dry shield suction and low section, Group C using extra-oral suction with high and low suction, and Group D using dry shield suction and extra-oral suction and low section. Difference between each categorical groups and particle, oral bacterial, fungus, and microbial air concentration will be tested using two-way ANOVA test or one way ANOVA test. Statistical analysis will be carried using STATA version 13.

2. Introduction

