3.7 Sample size

Total sample will be 120 subjects.

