3.8 Sampling technique

Multiple stage stratified random sampling at place level then subject randomly assign from schedule appointment using simple random sampling. Last stage, Simple random sampling of 40 subject at each 4 groups using computer-generated random numbers.

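### Hygienist experience and room distance are tested as patient-level predictors with no hygienist or room code and no allowance for clustering, so their p-values are too small if few, differing hygienists treat the 120 patients

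*Combined protocol and SAP*

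**What the plan says.** Section 3.10 gives the explanatory variables in two lists. The categorical list includes place and intervention group: "Place ,intervention groups, order of patient ,gender and supragingival calculus (mild, moderate, heavy". The continuous list includes age, procedure time and "year experience of hygienist, distance of room, humidity, and room temperature". Neither list contains a code for the hygienist or the room. Section 3.12 gives each participant a code but mentions none for operator or room.

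The particle outcome is one change score per patient, "difference in PN count[ΔPN ;post-test – pre-test , counts/ m³". Section 3.11 then states: "Multiple linear regression model will be built to predict particles count level with entrance value of 0.01 and exit value 0.101". It does not name the candidate predictors; I take them to be the explanatory variables of section 3.10. No random effect, cluster-robust error or operator factor is mentioned for this model or for the t tests and ANOVA.

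On numbers, section 3.7 says "Total sample will be 120 subjects" and the Abstract says "In each place 40 subject will be recruited". Section 3.8 describes "Multiple stage stratified random sampling at place level then subject randomly assign from schedule appointment using simple random sampling", so patients are randomised individually and place is the only stratum named. The number of hygienists and the number of rooms appear nowhere.

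**The concern.** A hygienist's years of experience hardly vary between that hygienist's patients. Room distance is not defined; if it is a fixed property of the room, the same holds. The information about such a variable comes mainly from the number of hygienists or rooms, whereas ordinary regression counts patients. If hygienists differ for any reason, such as how they handle the scaler or position the suction, the model can attribute those differences to experience and attach too small a p-value.

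At stake is a reported finding that operator experience or room layout drives aerosol exposure, which could influence staffing or clinic design when the data show only that some operators or rooms differ. Without identifiers recorded at the time, the problem may not be repairable at analysis.

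**Working it through.** **Inputs from the documents.** Total of 120 patients (3.7), matching 3 places × 40 = 120 (Abstract). Significance level 0.05, taken as two-sided, and regression entry value 0.01 (3.11). Section 3.8 also says "Simple random sampling of 40 subject at each 4 groups using computer-generated random numbers"; read literally that is 4 × 40 = 160, which conflicts with 120 and needs reconciling separately. I use 120, or 120/4 = 30 per group. No effect size, standard deviation or power is stated, so 120 cannot be reproduced from a power formula.

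**Assumptions, not in the documents.** K hygienists with equal caseloads m = 120/K; an ICC for the share of outcome variance lying between hygienists; no true effect of experience.

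**Formulas.** For a predictor constant within hygienist, the design effect is DE = 1 + (m − 1) × ICC. The effective sample size is 120/DE. The actual two-sided error rate is 2 × [1 − Φ(z/√DE)], with z = 1.96 at nominal 0.05 and 2.576 at nominal 0.01.

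Example, K = 6 and ICC = 0.10: m = 20, DE = 1 + 19 × 0.10 = 2.90, effective N = 120/2.90 = 41.4, 1.96/√2.90 = 1.151, error rate 25%.

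| K | m | ICC | DE | Effective N | Error at 0.05 | Error at 0.01 |
|---|---|---|---|---|---|---|
| 6 | 20 | 0.01 | 1.19 | 100.8 | 7.2% | 1.8% |
| 6 | 20 | 0.05 | 1.95 | 61.5 | 16% | 6.5% |
| 6 | 20 | 0.10 | 2.90 | 41.4 | 25% | 13% |
| 12 | 10 | 0.01 | 1.09 | 110.1 | 6.0% | 1.4% |
| 12 | 10 | 0.05 | 1.45 | 82.8 | 10% | 3.2% |
| 12 | 10 | 0.10 | 1.90 | 63.2 | 16% | 6.2% |

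At ICC 0, DE = 1 and there is no inflation. The entry value of 0.01 lowers the rates but does not bring them down to 1%.

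**Simulation check.** 6,000 trials per setting, 120 patients in four equal groups, experience drawn once per hygienist, and patient-level least squares with group in the model:

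- Place also in the model, 6 hygienists: 16.5% (ICC 0.05) and 27.1% (ICC 0.10) at nominal 0.05. With 12 hygienists: 11.0% and 15.7%. Adjusting for place therefore does not remove the problem when places have two or more hygienists.
- ICC 0: 4.5% to 5.0%.
- Regression of hygienist means on experience: 4.3% to 5.3% across all settings.

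**One hygienist per place (K = 3).** The columns for intercept, experience and two place indicators have rank 3 rather than 4, so experience and place cannot both be estimated. With place left out, the formula gives 25% (ICC 0.05) and 38% (ICC 0.10) at nominal 0.05.

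**Group comparison.** In the same simulations the test of one suction group against the reference group rejected in 4.7% to 5.4% of trials. Leaving out a factor that carries 5% or 10% of the variance raises the standard error by roughly 1/√0.95 = 1.026 or 1/√0.90 = 1.054, about 3% to 5%.

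**The case against.** The strongest reply is that this is a conditional problem in a peripheral analysis. None of the four objectives in section 2.3 concerns hygienist experience or room distance. Place, humidity and room temperature are also listed and may absorb part of the differences between rooms and sites. The particle outcome is a change from a reading taken shortly before the procedure, so stable room background cancels. With many hygienists, or hygienists who hardly differ, the inflation is small or absent.

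Much of this stands, and it limits the point to the p-values for experience and room distance. It does not remove it. Subtracting the pre-test reading does not cancel operator differences that arise during scaling, and the simulation shows inflation with place in the model. Nor does section 3.11 say that place is kept, since predictors enter and leave by p-value.

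A reader might go further and infer that only a handful of hygienists and rooms are involved, so that false predictors are bound to appear. The documents give no counts and no between-operator variance, so they do not support that. The 25% and 38% figures for three hygienists apply only if place is out of the model. A reader might also infer that the comparison of suction groups is invalid or biased. It is not: patients are randomised individually, and chance imbalance between operators is ordinary random error.

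**Conclusion.** The point holds conditionally. As written, the regression gives p-values for hygienist experience that are too small whenever few hygienists treat the 120 patients and those hygienists differ; the same applies to room distance if it is fixed per room. Under assumed ICCs of 0.05 to 0.10 and equal caseloads, the false-positive rate is about three to five times nominal with 6 hygienists and two to three times with 12. It disappears at an ICC of 0. With one hygienist per place, no model can separate experience from place. The main group comparison keeps its error rate and loses only a little precision. The change is worth making because it is cheap and the identifiers may be hard to recover later.

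**What to change.** In section 3.10, add a hygienist code and a room code for each patient, and state how many hygienists and rooms are expected.

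In section 3.11, include hygienist (within place) in the group comparison and the regression, either as a categorical factor or as a random intercept with small-sample degrees of freedom. Remove experience and room distance from the patient-level candidates. Describe them by hygienist and room, or analyse them at hygienist level if there are enough hygienists.

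The cost is two coded fields, no added patients or procedures, and the loss of a patient-level p-value for experience and room distance. As a fixed factor, hygienist uses K − 1 degrees of freedom in place of the 2 for place, so 3 more with 6 hygienists (5 − 2) and 9 more with 12 (11 − 2). Balancing allocation within hygienist is optional. It would add some precision, but exactly equal groups need caseloads in multiples of four, which 12 hygienists with 10 patients each could not meet.

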3.11 Statistical consideration

All continuous variables will be express as mean and stander deviation

All categorical variables will be described as frequency and percentage

Difference between baseline and during of procedure measurement intended for particle, oral bacteria, fungus and microbial air concentration will be calculating using pairwise t test.

Difference between each categorical groups and particle, oral bacterial, fungus, and microbial air concentration will be tested using two way ANOVA test or one way ANOVA test

Strength and direction of association between particle count levels and time of procedure will be tested using correlation test

Multiple linear regression model will be built to predict particles count level with entrance value of 0.01 and exit value 0.101. Confidence level of 95% will be computed and p-value less than 0.05 will be considered as significant.

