2.2 Rational of research

Most of the previous studies used a low numbers of sample size and the majority of them were conducted in vitro. In addition, they assessed either amount of bacteria or particles comparing EOS to baseline.

In this study, we will analyze particles count and microorganisms comparing EOS to dryshield, combined group and standard group.

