2.3 Objective

1. Measure particles, bacteria and fungus that arising from patient's mouth in each group.
2. Evaluate health exposure risk for each group to baseline reading (pre-test).
3. Compare health exposure risk for each group to standard group (Group A)
4. Compare health exposure risk between each of the following groups A, B , C and D.

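### Objectives 3 and 4 ask which suction groups differ, but Section 3.11 plans only an overall ANOVA, with no between-group pairwise procedure, no adjustment and no formally named primary outcome

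*Combined protocol and SAP*

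**What the plan says.** **The comparisons wanted.** Section 2.3 sets them out in advance. Objective 3 is "Compare health exposure risk for each group to standard group (Group A", which is three pairs. Objective 4 is "Compare health exposure risk between each of the following groups A, B , C and D", which is six pairs and includes those three. Section 2.2 describes the purpose in the same way: "comparing EOS to dryshield, combined group and standard group".

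**The analysis offered.** Section 3.11 states that group differences in particle, "oral bacterial, fungus, and microbial air concentration will be tested using two way ANOVA test or one way ANOVA test". The Abstract repeats this and adds nothing: "microbial air concentration will be tested using two-way ANOVA test or one way ANOVA test". The only decision rule is "p-value less than 0.05 will be considered as significant".

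**Neighbouring analyses.** Section 3.11 also has a t test called pairwise, but its subject is "Difference between baseline and during of procedure measurement intended for particle" and the other measurements, that is, before against during. There is also a regression: "Multiple linear regression model will be built to predict particles count level with entrance value of 0.01 and exit value 0.101".

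**Outcomes.** Section 3.10 lists particle count change, oral bacteria, fungus, and microbial air at the floor and air conditioner. None is called primary. Section 2.1, however, regards particle number as the closer indicator of exposure risk to health, and that risk is the quantity named in objectives 2 to 4.

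**The concern.** A significant F test says that the four group means are not all equal. It does not say whether extra-oral suction beats standard suction, whether it beats dryshield, or whether the combination adds anything. Those are the questions in objectives 3 and 4.

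To answer them, someone must add a pairwise step that the plan does not contain. The pairs are fixed in advance, but the test, its adjustment and the model behind it could be chosen after the data are seen. The outcome that decides is not formally fixed either. Section 3.13 says that neither subject nor observer can be blinded, which makes it more useful to settle these choices beforehand.

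**Working it through.** **1. Does any section supply the pairwise step?**

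| Element | What it compares | Answers objectives 3 and 4? |
|---|---|---|
| One-way or two-way ANOVA (3.11, Abstract) | All group means at once | No: does not identify pairs |
| Pairwise t test (3.11) | Before against during | No: this is objective 2 |
| Correlation (3.11) | Particle count and procedure time | No |
| Regression (3.11) | Predictors of particle count, with entry and exit thresholds | No: no reference group or contrast is fixed, selection may drop group, and it covers one outcome |

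No section supplies it.

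**2. The plan's own figures.** It gives no power, effect size or error rate for group comparisons. Its total of 120 (Section 3.7) agrees with 3 places × 40 (Abstract). Divided equally over four groups this is 120/4 = 30 per arm. Section 3.8 can also be read as 40 per group (4 × 40 = 160), so 40 is shown as a variant.

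**3. What an unspecified pairwise step could do.** Assumptions, not in the documents: normal data, equal variances, 30 per arm, one outcome, one-way model with 4 × 29 = 116 degrees of freedom. The statistic for a pair is t = (difference in means) / (s × √(2/30)). Simulated chance of at least one false claim:

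| Pairwise rule | All four groups equal | Only A differs: false claim among B, C, D |
|---|---|---|
| Unadjusted pairs after a significant F test | 5% | 10% (A shifted 0.5 SD); 12% (0.8 SD or more) |
| Tukey, all six pairs | 5.0% | 2.8% |
| Six unadjusted pairs, no F test | about 20% | – |
| Three unadjusted pairs against A, no F test | about 12.5% | – |

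A group-plus-place model changes the unadjusted and F-gated rates by about 0.1 to 0.2 of a point. With 40 per arm these rates move by at most about 1 point.

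The first row shows that an F test in front of the pairs protects when all groups are equal. It does not protect when one group truly differs, because the F test is then likely to be significant and the remaining pairs are tested at 0.05 each.

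**4. Across outcomes.** Taking particle count, oral bacteria and fungus as the efficacy outcomes, the chance that at least one F test is falsely significant is 1 − 0.95³ = 14.3% if the outcomes are independent, and less if they are correlated. It matters only if a positive result on any one of them would be presented as effectiveness.

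**5. Price of Tukey** (group-plus-place model, 120 − 4 − 2 = 114 degrees of freedom, 30 per arm, √(2/30) = 0.258):

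| | Unadjusted | Tukey |
|---|---|---|
| Critical t for a pair | 1.98 | 2.61 |
| Half-width of 95% interval = critical t × 0.258 | 0.51 SD | 0.67 SD |
| Difference detectable with 80% power | 0.73 SD | 0.89 SD |
| Power at 0.73 SD | 80% | 59% |
| Detectable difference, 40 per arm | 0.63 SD | 0.77 SD |

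**The case against.** **The plan never says that pairs will be run unadjusted.** This is right. A reader might infer that the plan carries a 20% false-claim rate. The documents do not support that: the written test is an F test at 5% per outcome, and the 20%, 12.5% and 10 to 12% figures describe analyses that someone would have to add. They illustrate what the gap permits.

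**The outcomes are not wholly unranked.** This also stands in part. A reader might infer that nothing indicates which outcome counts. Section 2.1 ties exposure risk to particle number, and particle count alone has a change formula (3.10) and its own regression (3.11). That is a strong pointer, but it is not a designation as primary, and Section 3.11 tests all the outcomes under the same rule.

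**How many outcomes?** Sections 3.10 and 3.11 list and test the floor and air-conditioner samples as well, so one might count four F tests, giving 1 − 0.95⁴ = 18.5%. Section 3.4, however, introduces these samples to control for organisms coming from the air conditioner. Three efficacy outcomes and 14.3% are the fairer count.

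**One-way or two-way may not be an open choice.** The ANOVA sentence may cover every categorical variable in Section 3.10, with the form depending on the factors. That is a possible reading. It still does not say which model gives the intervention comparison.

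**Tukey is not the only valid method.** For objective 3 alone, Dunnett's method needs t of about 2.38, with power of about 67% at 0.73 SD rather than 59%. It does not cover the six pairs of objective 4.

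**Conclusion.** The point holds. As written, the group analysis cannot answer two of the four objectives. The pairwise procedure and its adjustment are absent, and no outcome is formally primary. This rests on the text alone and needs no assumption.

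The size is illustrative and rests on the normality, equal-variance and sample-size assumptions given above. The realistic exposure is the sequence of F test and then unadjusted pairs: about a one-in-eight to one-in-ten chance, on one outcome, of falsely separating the three non-standard groups when only A differs. Particle and colony counts may be skewed, so the actual rates and power could differ.

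This should be corrected before group comparisons are run. It does not call the randomisation or data collection into question.

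**What to change.** In Section 3.11:

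- **Primary outcome.** Name the particle count change, in line with Section 2.1, or another single outcome of the sponsor's choice.
- **Group comparison.** Answer objectives 3 and 4 with Tukey-adjusted comparisons of all six pairs and simultaneous 95% confidence intervals. Take them from one prespecified group-plus-place model, since Section 3.8 stratifies by place. The three pairs with A answer objective 3 and all six answer objective 4. The F test may be reported but is not the basis for a pairwise claim.
- **Secondary outcomes.** Report oral bacteria and fungus from the same model, stating whether the response is the during-procedure value or the change. Give 95% intervals and make no significance claims unless these are adjusted.
- **Floor and air-conditioner samples.** Report them as the control measure described in Section 3.4.

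The cost is the loss of precision and power shown in the last table of the working: pairwise intervals about a third wider (0.67/0.51 = 1.31), and differences between 0.73 and 0.89 SD no longer detectable with 80% power at 30 per arm. Otherwise only the wording of the analysis section changes.
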